### **3. JUSTIFICATION FOR THE ADDENDUM**

Since the OMS declared the COVID-19 pandemic, various challenges exist which result in restrictions of visits to healthcare facilities, increased demands on the health services and changes to trial staff availability and resources. Participants may also be required to self-isolate, which introduces difficulties for Investigators to maintain medical oversight. These challenges could have an impact on the conduct of trials and data integrity, such as the completion of trial assessments, completion of trial visits, continued patient safety oversight and the provision of Investigational Medicinal Products (IMPs).

As a sponsor, Reata Pharmaceuticals is committed to ensuring the safety of trial participants, maintaining compliance with good clinical practice (GCP), and minimizing risks to trial integrity.

To face this evolving situation, Reata Pharmaceuticals has put in place some pragmatic actions to address the challenges of conducting research, and in ensuring the rights, safety and wellbeing of participants.

This addendum outlines Reata Pharmaceuticals' strategies to be implemented during the COVID-19 pandemic, to maintain ongoing safety reporting, access to study drug, continuity of patient care, and oversight of clinical site performance and quality.

This document is being presented in an effort to make available information regarding the mitigation strategies that have been implemented for the CARDINAL study as a result of COVID-19. Of course, since the nature and scope of this outbreak is rapidly evolving, Reata continues to monitor the situation and adjust its response as appropriate.

The main activities this addendum addresses are:

- ongoing safety monitoring of the trial participants
- continuity of IMP supply for patients
- preservation of trial integrity through the collection of critical data

#### 4. CHANGES TO THE CURRENT APPROVED PROTOCOL

THE FOLLOWING CHANGES ARE IMPLEMENTED DURING THE COVID-19 PANDEMIC. AS THE IMPACTS OF COVID RESOLVE, THE CURRENTLY APPROVED VERSION OF THE PROTOCOL WILL BE FULLY REIMPLEMENTED FOR STUDY CONDUCT. AS SUCH, THESE CHANGES ARE PRESENTED AS AN ADDENDUM TO BE FOLLOWED, AS NEEDED AND DURING THIS GIVEN PERIOD ONLY.

	VERSION NUMBER	VERSION DATE
CURRENT APPROVED PROTOCOL:	4.0 (FR, SP, UK)	23 May 2019
CHANGES TO THE CURRENT APPROVED PROTOCOL		
1.	SECTION NO., SECTION TITLE, PAGE NO.(S):	7. INVESTIGATIONAL PLAN page 33
	OLD TEXT:	No changes
	NEW TEXT:	
Added: new subparagraph 7.6: Home Health Provider Use
 
Due to the COVID-19 outbreak and the resulting restrictive measures put in place by the different national governments that in many cases resulted in travel restrictions, limited availability of site access and personnel, and local limitation on the movement of individuals delegated, in order to guarantee the rights, safety and wellbeing of participants and of the trial sites' staff, the Sponsor implemented the use of a home health group in the EU to assist with the collection of study required visits and laboratory assessments for the CARDINAL study. The use of a company specialized in home health services ensures the ongoing safety monitoring of trial participants and maintaining trial integrity through the collection of critical data, in accordance with EMA and local guidelines about the COVID-19 pandemic management. Different companies have been approached, all of them specialized in providing health professionals (Certified Mobile Research Nurses – CMRN) experienced in supporting investigators in conducting certain activities related to clinical trial conduct. For each hired CMRN, the site will be provided with the following documentation: signed and dated CV, Nursing Licensure, GCP training certificate, and protocol training certificate. The CMRN will also be included in the Delegation of Activities log of the site.

		
The tasks delegated to the CMRN at the patient's home will be: collection of vital signs and weight measurements, collection of information about Adverse Events and concomitant medications, collection of laboratory samples (blood and urine), supply of urinary pregnancy test for self-reading, drug accountability, and diary collection.
 
The laboratory samples are collected using the laboratory kit provided by the centralized laboratory normally used for the study, and are processed and shipped according to the laboratory manual of the study.
 
All costs relevant to these additional services will be covered by Reata Pharmaceuticals.

	REASON FOR CHANGE:	Mitigation measures taken by the Sponsor to ensure safety of subjects and trial's integrity.
2.	SECTION NO., SECTION TITLE, PAGE NO.(S):	9.10.11. Physical Examination page 53
	OLD TEXT:	No changes
	NEW TEXT:	
Additional sub-paragraph 9.10.11.1: Short Physical assessment during the COVID-19 outbreak:
 
The home health agency appointed by the Sponsor to support visit conduct and patient safety management will only perform assessments critical to safety monitoring (see below). Staff will be trained, and training documented, on the following applicable protocol specific visit procedures:
 
 
o Vital sign measurements (e.g., blood pressure, heart rate, etc.)
 
o Adverse Event/Concomitant Medication collection
 
o Weight measurement
 
o Laboratory sample collection (blood/urine) and processing
 
o Urine Pregnancy testing (for women of childbearing potential)
 

	REASON FOR CHANGE:	Mitigation measures taken by the Sponsor to ensure safety of subjects and trial's integrity.
3.	SECTION NO., SECTION TITLE, PAGE NO.(S):	9.10.12. Pregnancy Test page 53
	OLD TEXT:	No changes
	NEW TEXT:	
Added: new subparagraph 9.10.12.1 Self reading pregnancy test:
 
During the emergency, urinary pregnancy test for self-reading will be

		provided by the CMRN coming to patient's home. Results will be transmitted to the site investigators.
	REASON FOR CHANGE:	Mitigation measures taken by the Sponsor to ensure safety of subjects.
	SECTION NO., SECTION TITLE, PAGE NO.(S):	9.10.14. Study Drug Dispensation and Collection page 54
	OLD TEXT:	No changes
4.	NEW TEXT:	
Added subparagraph 9.10.14.1 Study drug distribution during the COVID-19 pandemic. Prior to the COVID-19 pandemic, trial participants were assigned and dispensed IMP during study site visits. During the study site visits, trial participants are sent home with IMP and instructed to self-administer the IMP each day until their next on-site study visit, at which they would return any unused IMP. As the trial participants have been responsible for IMP storage within their homes, as well self-administration of the IMP throughout the study, they are well acquainted with these facets of the study. For those trial participants who discontinue physical site visits during COVID-19, distribution of IMP may be made directly to the trial participants' homes by shipment from investigator, through the Hospital pharmacy. IMP distributed in this manner will be shipped via traceable courier as an expedited shipment.
 
Given the stability profile of bardoxolone methyl capsules under multiple temperatures and relative humidity conditions, short term temperature excursions above 30°C and as low as 15°C during storage are acceptable.
 
For IMP shipments to trial participants' homes, investigators will monitor the time from shipment to receipt of the IMP by the trial participant. In the absence of temperature monitoring, and if shipping time exceeds 48 hours, the investigator will immediately instruct the patient not to use the IMP until further guidance is provided. The investigator site will then contact Reata (the sponsor) to determine whether the shipment may be used or must be replaced. The investigator site will contact the patient as to the disposition of the IMP.
 
Investigators will remain in close contact with trial participants receiving IMP at their home and, if necessary, will provide any instructions needed on the use of the IMP. Accountability of the IMP

		for these trial participants will be conducted by home health nurses during home visits. After accountability is complete, the home health nurse will secure the kits in a bag that will be returned to the site when the trial participant is able to return to the site for their next visit. The trial participant will be instructed not to take any additional IMP from the kits that have been placed in the plastic bag.
	REASON FOR CHANGE:	Mitigation measures taken by the Sponsor to ensure safety of subjects.
5	SECTION NO., SECTION TITLE, PAGE NO.(S):	10.4. Study Drug Administration page 58
	OLD TEXT:	No changes
	NEW TEXT:	Added subparagraph 10.4.1 Intake of IMP Beyond Week 100 during the COVID-19 outbreak. The Week 100 visit (Day 700 +/- 3 days) serves to collect the final “on treatment” lab values from patients. To minimize any days off drug prior to the Week 100 visit, and given the evolving situation of COVID-19, sites may extend dosing by 1 week beyond the protocol window for the Week 100 visit. The maximum extension in dosing is to study Day 710 (Day 707 +/- 3 days), unless otherwise approved by Reata and the EC. The Week 104 visit must be adjusted accordingly to ensure the Week 104 labs are collected 4 weeks after completing the end of treatment (last dose).
	REASON FOR CHANGE:	Mitigation measures taken by the Sponsor to ensure safety of subjects.
6.	SECTION NO., SECTION TITLE, PAGE NO.(S):	15.3. Written Informed Consent page 71
	OLD TEXT:	No changes
	NEW TEXT:	Additional sub-paragraph 15.3.1: Informed Consent for Home Health Services: A home health services provider to support visit conduct and patient safety management during this period has been appointed by the Sponsor. An ICF letter has been created and provided to the EC for approval in participating countries. Approval of the revised consent form will allow sites to obtain verbal permission from the study patient to share their contact information with the home health services company and to conduct the study visit.
	REASON FOR CHANGE:	Among mitigation measures taken by the Sponsor to ensure safety of subjects.
7.	SECTION NO., SECTION TITLE, PAGE NO.(S):	15.6. Protocol Deviations page 73

	OLD TEXT:	No changes
	NEW TEXT:	
Additional subparagraph 15.6.1 Deviation during the COVID-19 Outbreak: Any data that cannot be assessed remotely will be noted as missing. All deviations due to the impacts of COVID-19 will be identified and documented accordingly by the site and the Sponsor.
 
The failure to complete a protocol visit will not be considered as a reason for study discontinuation and, beyond the necessary documentation (e.g., duly documented in patient's note by the Investigator), will not be considered as a major deviation that must be notified to the Competent Authority according to GCP § 5.20.
 
Deviations will be reported, evaluated, and discussed according to the study plan and in the final study report.

	REASON FOR CHANGE:	As allowed by EMA and local guidelines for management of clinical trials during the COVID-19 outbreak.

## **5. CHANGES IN OTHER STUDY-RELATED DOCUMENTS**

### **5.1. Informed Consent**

An ICF letter has been created and provided to the EC for approval in participating countries. Approval of the revised consent form will allow sites to obtain verbal permission from the study patient to share their contact information with the home health services company and conduct of the study visit. After verbal agreement is obtained, written permission can be obtained at the next on-site study visit.

## **6. APPENDICES**

List of memos provided to the study sites:

1. Initial COVID-19 Guidance dated 10 March 2020
2. IP shipping instructions dated 17 March 2020
3. Lab Kit Shipping Instructions dated 19 March 2020

## 1. LIST OF ABBREVIATIONS

**Table 1: List of Abbreviations**

Abbreviation	Term
COVID-19	Coronavirus Disease 2019
eGFR	estimated glomerular filtration rate
FDA	Food and Drug Administration
IP	Investigational Product
SAP	Statistical Analysis Plan
SARS-CoV-2	Severe Acute Respiratory Syndrome Coronavirus 2

## 2. RATIONALE FOR ADDENDUM

This addendum describes clarifications to the Statistical Analysis Plan (SAP) version 3.0 as well as additional analyses for Year 2 of CARDINAL Phase 3 to characterize the impact of the COVID-19 pandemic on the trial.

## 3. CORRECTION AND CLARIFICATION TO THE SAP

### 3.1. Correction to Covariate Computation

Analyses of efficacy will adjust for the duration of exposure to drug within each year of the study. The fraction of expected exposure duration for Year 2 analyses (i.e., Week 100 and Week 104), calculated as the fraction of expected exposure duration in Year 2, will be included in analyses as a covariate. As outlined in Section 6.5.11 of the SAP, fraction of expected exposure in Year 2 (TRT\_EXP2) is calculated using the date of last dose in Year 2. However, any patient who permanently discontinued treatment in Year 1 would not have a Year 2 date of last dose. As a result, the definition has been corrected to use the date of last dose in the study, allowing all randomized patients to have a TRT\_EXP2 value and therefore contribute to analyses. Additionally, the length of exposure was extended from 700 to 707 days to account for the COVID-19 protocol modification, which allowed longer dose administration. The computation was also corrected by adding “+1” to the date of last dose. See Table 2 for the corrected definition of TRT\_EXP2.

**Table 2: Computation of Fraction Received of Expected Two-Year Exposure**

SAP definition	Corrected definition
$[(\text{date of last dose in second year}) - (\text{date of first dose})] / 700$	$[(\text{date of last dose} + 1) - (\text{date of first dose})] / 707$

### **3.2. Clarification of Hierarchical Testing Strategy**

Section 8.4 of the SAP specifies that all endpoints tested at Year 1 and Year 2 will use a significance level of 0.025. Within each year, endpoints are tested following a fixed-sequence hierarchical testing strategy. The total significance level (0.05) was split between Year 1 and Year 2 as a strategy to reserve alpha to test Year 2 if the Year 1 testing sequence was not statistically significant. Formal testing in the sequence may proceed so long as statistically significant evidence of benefit continues to be shown. If in the sequence one endpoint does not show statistically significant evidence of benefit, formal statistical testing of subsequent endpoints will not occur.

As a clarification to the SAP, if there is a significant treatment effect for both Year 1 endpoints, then the significance level for Year 1 (0.025) remains available to be carried forward (recycled or passed along) to the Year 2 testing sequence. Thus, if both Year 1 endpoints are significant, the Year 2 testing sequence will be tested using a significance level of 0.05. This approach aligns with the fixed-sequence method in FDA guidance (Multiple Endpoints in Clinical Trials., January 2017).

## **4. COVID-19 IMPACT**

FDA recognizes that the COVID-19 public health emergency may impact the conduct of clinical trials of medical products (FDA Guidance on Conduct of Clinical Trials of Medical Products during COVID-19 Public Health Emergency, September 2020). COVID-19 posed significant challenges to study conduct, which were not unique to the 1603 Phase 3 study including site closures and access restrictions, and quarantines for site personnel and patients creating barriers to scheduling and conducting visits according to the protocol specified schedule. Additionally, the 1603 Phase 3 study population has chronic kidney disease and is therefore categorized as vulnerable and at higher risk for developing serious complications from COVID-19. Specific guidance for these individuals varied over time and by geography, but as a group they were generally advised by health officials to not be in close physical contact with other people (<https://www.cdc.gov/coronavirus/2019-ncov/need-extra-precautions/index.html>).

This addendum makes the following modifications to the analysis and adds additional analyses to address the impact of COVID-19 on the 1603 Phase 3 study.

### **4.1. Changes in Study Conduct**

Changes to study conduct due to COVID-19 are recorded in the clinical database for each patient. The overall number and percentage of patients impacted by COVID-19 will be summarized and listed. The impact of COVID-19 on study visits (e.g., not done or done outside the window), assessments (e.g., not performed), data collection method (e.g., telephone, video conference, home health, and local lab) will be listed.

### **4.2. Additional Disposition Categories**

Categories for end-of-treatment and end-of-study reasons were added to data capture and disposition summaries:

- Terminated early from the treatment because of COVID-19; and
- Terminated early from the study because of COVID-19.

### 4.3. Protocol Deviations

Deviations due to the impacts of COVID-19 are documented in the clinical database by the site and the Sponsor. These deviations will be identified in the protocol deviations data and presented in a data listing.

### 4.4. Changes to Key Efficacy Analyses

COVID-19 created logistical challenges associated with study execution, including possible interruptions in treatment due to quarantine and travel restrictions as well as closure or reduced operating hours of sites/institutions. Many patients enrolled in the 1603 Phase 3 study had to travel long distances requiring full day or overnight travel for in-clinic visits. The National Kidney Foundation advised clinical trial participants to avoid using public transportation when possible (<https://www.kidney.org/covid-19>). Shipping drug directly to patients and home healthcare visits were added as options to keep patients on treatment per-protocol and overcome limitations associated with travel. High demand for home health nurses during this global pandemic and varying levels of patient comfort with home health nurse interactions during quarantine created continued challenges and limitations with scheduling flexibility.

Key efficacy analyses were modified as follows to address these issues related to COVID-19.

#### 4.4.1. Extended Visit Windows

The Week 100 visit serves to collect the final “on treatment” lab values (including eGFR) from patients. Given the aforementioned logistical challenges due to COVID-19, the protocol was amended to allow up to a two-week extension in the protocol-specified window for the Week 100 visit to increase scheduling flexibility, as needed. As a result, some patients were shipped additional study drug kits so that patients could continue treatment despite their delayed Week 100 visits. Accordingly, some patients were dosed for up to 2 additional weeks and the Week 100 analysis window was adjusted to account for the extended dosing as specified in Table 3.

**Table 3: Analysis Window for Week 100 Visit**

Patient Treatment Status	Target Study Day a	Week 100 Analysis Window	
		Original b	Adjusted
Permanently discontinued treatment prior to Week 100	700	$659 \leq \text{study day} \leq 714$	No change
Completed treatment at Week 100	700 c	$659 \leq \text{study day} \leq 714$	$659 \leq \text{study day} < 728$ ; and Week 100 $\leq 13$ days after last dose

a Study day is relative to the date of randomization (SAP Section 6.5.2)

b Original Week 100 analysis window defined in SAP Section 6.5.11, Table 3

c Target study day extended by up to 14 days to account for additional drug dispensed prior to Week 100

Scheduling of the Week 104 visit was adjusted for patients with extended dosing duration to ensure that the Week 104 eGFR value is collected 4 weeks after last dose. The SAP-specified

analysis window of 14 to 35 days with a protocol-specified target of 28 days after the last dose, which was reinforced by the Sponsor, did not allow much flexibility in scheduling. The Week 104 analysis window was extended by removing the upper bound on days after last dose (Table 4) to avoid exclusion of available values collected beyond the original analysis window. If eGFR is assessed more than once within the visit window, the measurement that is closest to 28 days after last dose (i.e., 4-weeks after the last dose as specified in the protocol) is used for the purpose of data analysis.

**Table 4: Analysis Window for Week 104 Visit**

Target Days After Last Dose a	Week 104 Analysis Window	
	Original b	Adjusted
28	14 ≤ days after last dose ≤ 35	days after last dose ≥ 14

a Days after last dose in second-year dosing interval. Patient must have been dispensed treatment in the second year, otherwise Week 104 is considered missing.

b Original Week 100 analysis window defined in [SAP Section 6.5.4, Table 3](#)

#### 4.4.2. Accounting for Regional Differences

Study 402-C-1603, Phase 3, is a global clinical trial. The regional emergence and impact of COVID-19 is heterogeneous across the various countries contributing participants to the trial. Region (US; non-US) is added as a covariate to the models assessing Week 100 and Week 104 to account for differential COVID-19 impact by region.

#### 4.4.3. No Changes Due to Temporary Interruptions in Study Treatment

A COVID-19 appendix was added to the study protocol to allow for temporary interruptions in study treatment. No changes are required for analyses of Week 100 or Week 104 due to temporary discontinuation and reinitiation of study drug given how the key efficacy analyses were defined:

- Analyses of Week 100 are based on target study day, irrespective of whether or not a patient is receiving study drug.
- Analyses of Week 104 are based on days after final dose following permanent study drug discontinuation in the second year. Analyses of Week 104 data will not include data collected during any intermediate off-treatment period.

#### 4.5. Data Handling for Assessments After Positive COVID-19 Diagnosis

Recent studies have documented that COVID-19 can cause damage to multiple organs, such as the heart, liver, kidneys, and the immune system ([Chen, 2020](#); [Wang, 2020](#)). Therefore, the summary tables and analyses do not include efficacy and safety data (clinical laboratory [including eGFR], vital sign, electrocardiogram, visual acuity, and audiology assessments) collected after the start date of adverse event preferred term “coronavirus”. If the number of patients with positive COVID-19 diagnosis is sufficiently large, the data collected for these patients may be summarized together. All data will be presented in by-patient listings.

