#### **4.6. Pre-COVID Era and Post-COVID Era Comparison**

As an additional analysis, the pre-COVID era which will include all Week 100 and Week 104 visits that were planned on or prior to March 1, 2020 will be compared to the same visits that were planned post March 1, 2020.

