This SAP was finalized, approved by the Sponsor, and placed on file before database lock. This version of the SAP describes the analyses planned prior to the database lock. Unless otherwise specified, the CSR will summarize these analyses. Any substantive changes made to the SAP

after the database lock will clearly be identified in the CSR, and any analyses in addition to those specified in the SAP prior to the database lock are considered ad hoc.

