## **6. GENERAL CONSIDERATIONS FOR DATA ANALYSES AND HANDLING**

The efficacy and safety analyses use the analysis sets defined in Section 6.3. Patient listings (as appropriate) of all analysis data that support summary tables and/or figures are provided along with their source data. The summary tables do not include measurements from patients excluded from the pre-defined analysis sets or extra measurements (such as unscheduled or repeat assessments) not closest to the target study day unless specified otherwise, but the patient listings do include these data. Missing data are not imputed, unless otherwise specified. In general, patient listings are sorted by patient number and assessment date (time and parameter, as applicable). Any laboratory value (including eGFR), vital sign assessment, or ECG value collected after starting dialysis or after receiving a kidney transplant is considered invalid and will be treated as missing.

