### **8.8.3. Summary of Sensitivity Analyses of the Primary Efficacy Endpoint – Year 2**

The following sets of sensitivity analyses are summarized in tables and forest plots: tipping point with multiple imputation, control-based imputation, MMRM fit to the as-treated population, and MMRM fit to the per protocol population.

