### **8.9.2. Sensitivity Analyses**

Sensitivity analyses described in Section 8.7.2 are performed to assess the robustness of conclusions of the 2-year key secondary efficacy endpoint. The following sets of sensitivity analyses are summarized in tables and forest plots: tipping point with multiple imputation, control-based multiple imputation, and the ANCOVA model fit to the per protocol population (Year 2).

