##### 9.1.1.1. All Available Data

Changes in eGFR for the bardoxolone methyl group compared to the placebo group are evaluated at Week 48 as the Year 1 primary endpoint, and are evaluated at Weeks 1, 2, 4, 6, 8, 12, 24, and 36 as exploratory analyses using the statistical model defined in Section 8.6.1.

Changes in eGFR for the bardoxolone methyl group compared to the placebo group are evaluated at Week 100 as the Year 2 primary endpoint, and are evaluated at Weeks 64, 76, and 88 as exploratory analyses using the statistical model defined in Section 8.8.1.

Analyses of eGFR using all available data use all eGFR values collected, irrespective of whether or not a patient is receiving treatment.

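### SAP Addendum 4.5 removes measured post-COVID eGFR and safety values from the Year 2 tables and analyses, and no named analysis keeps them

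*SAP*

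**What the plan says.** SAP Addendum Section 4 introduces its contents with "This addendum makes the following modifications to the analysis". Section 4.5, citing evidence that COVID-19 can damage several organs including the kidneys, then says "the summary tables and analyses do not include efficacy and safety data" if collected after the start date of the coronavirus preferred term. The list covers clinical laboratory values (eGFR named), vital signs, ECG, visual acuity and audiology. Nothing ends the exclusion on recovery or limits it by severity. If enough patients are affected (no number is set), their data may be summarized together. Everything is listed by patient.

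The main SAP takes another line. Section 8.8.1 feeds every eGFR value collected through Week 100 into the primary model. The opening of Section 9 lets every value within its visit window contribute, with dialysis as the one exception. Section 9.1.1.1 says: "Analyses of eGFR using all available data use all eGFR values collected, irrespective of whether or not a patient is receiving treatment". Section 6 has one general rule for setting values aside: a laboratory, vital sign or ECG value after dialysis or transplant "is considered invalid and will be treated as missing".

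For Week 100, Section 8.8.3 names these sensitivity analyses: "tipping point with multiple imputation, control-based imputation, MMRM fit to the as-treated population, and MMRM fit to the per protocol population". For Week 104, Section 8.9.2 names tipping point, control-based multiple imputation and per-protocol.

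**The concern.** COVID-19 arises after randomization. Removing every later measurement changes the question the Year 2 comparison answers: it no longer covers outcomes after infection, although those outcomes were measured. That can be a legitimate choice. But the plan commits to no version with the values kept, so the report need not show whether the choice mattered.

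The safety side is more direct. SAP Section 3.1.2.1 makes safety through Week 104 a Year 2 primary endpoint. Sections 10.5.2, 10.5.2.1 and 10.8 count patients who cross laboratory or ECG thresholds at any point in the study. Under Addendum 4.5 a crossing first measured after infection drops out of those by-arm counts. The stated reason, organ damage from the infection, concerns attribution. It does not explain why by-arm safety tables should omit the measurement, in a population that Addendum Section 4 itself describes as at higher risk of complications.

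**Working it through.** **1. Does any named Year 2 analysis use the excluded values?**

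- *Tipping point* (8.6.2.1 and 8.7.2.1, applied to Year 2 by 8.8.2 and 8.9.2): imputes missing values and shifts those in the bardoxolone arm. It tests how far missing values could overturn a result, but does not use measured ones.
- *Control-based imputation* (8.7.2.2 for its form): draws from placebo data in place of the measurement.
- *As-treated and per-protocol* (8.6.2.2, 8.6.2.3, 8.7.2.3): restrict values or patients further.
- *Era comparison* (Addendum 4.6): visits planned up to March 1, 2020 "will be compared to the same visits that were planned post March 1, 2020". The split is by planned date, not infection, and nothing says excluded values return.
- *All-available-data eGFR* (9.1.1.1): would keep them on its own wording, but Addendum 4.5 covers analyses without exception. The two texts conflict.
- *Further analyses as appropriate* (8.6.2, 8.7.2): allowed, but under Section 2.2 "any analyses in addition to those specified in the SAP prior to the database lock are considered ad hoc".

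So no named analysis clearly keeps them.

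**2. The plan's own precision figure (Section 4.3.2).** Inputs: 78 and 79 patients (4.3.1), SD 8, two-sided alpha 0.025, two-sample t-test. Standard error = 8 × √(1/78 + 1/79) = 1.277. By the noncentral t, power is 80.7% at 4.0 and 50.4% at 2.9, against 80% and 50% stated. The plan's figures reproduce. The difference at exactly 80% power is 3.97.

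**3. Precision lost by excluding.** The share affected, c, is not in the documents; 2–10% is assumed. Worst case for Week 104: imputation recovers nothing, so each arm has 78.5 × (1 − c) patients and the standard error grows by 1/√(1 − c).

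| c | Patients (157c) | SE factor | Week 104 difference at 80% power |
|---|---|---|---|
| 0 | 0 | 1.000 | 3.97 |
| 2% | 3.1 | 1.010 | 4.01 |
| 5% | 7.9 | 1.026 | 4.07 |
| 10% | 15.7 | 1.054 | 4.19 |

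The Week 100 repeated-measures model loses less if only that visit is dropped. With the planning correlation of 0.7 and 12 earlier post-baseline visits, R² = 12 × 0.49/(1 + 11 × 0.7) = 0.676. The factor √(R² + (1 − R²)/(1 − c)) is 1.003, 1.008 and 1.018.

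**4. Possible shift in the treatment estimate.** This is a simple-mean approximation. In each arm let f be the share affected and L the amount by which affected patients' eGFR change falls below that of the others. Keeping rather than dropping the values changes the bardoxolone-minus-placebo estimate by −(f_B × L_B − f_P × L_P).

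| f_B | f_P | L_B | L_P | Shift |
|---|---|---|---|---|
| 5% | 5% | 5 | 5 | 0 |
| 5% | 5% | 10 | 5 | −0.25 |
| 5% | 2% | 5 | 5 | −0.15 |
| 5% | 0% | 10 | – | −0.50 |
| 10% | 5% | 10 | 5 | −0.75 |
| 10% | 0% | 10 | – | −1.00 |

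Swapping the arms reverses the sign. With equal shares f, a shift of 1 requires L_B and L_P to differ by 1/f: 50 at 2%, 20 at 5%, 10 at 10%. With unequal shares much less is needed: in the last row about 5% of the trial is affected, and a 10-point loss is enough.

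**5. Safety counts.** One omitted threshold patient changes an arm's incidence by 1/78 = 1.28 or 1/79 = 1.27 percentage points.

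**The case against.** The strongest defence is that the exclusion is written down in advance and reasoned: an infection reported to injure kidneys could obscure the drug's effect. Section 6 already sets aside values after dialysis or transplant. Adverse events and serious adverse events are not in the excluded list and stay tabulated by arm (Sections 10.1 and 10.1.2). Addendum 4.1 summarizes how many patients COVID-19 affected, and the final report carries listings and narratives (Section 5.2). If the excluded values count as missing, tipping-point and control-based analyses do stress the result.

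Much of this stands. It supports the exclusion as one permissible analysis, and limits the safety loss to measurements not reported as adverse events. It does not supply a comparison that uses the measured values, and stress-testing imputed values is a weaker check when the real ones are in the database. Addendum 4.1 counts patients affected by COVID-19 in any way; it does not promise excluded values by arm.

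Three stronger readings are tempting but unsupported:

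- *That the intention-to-treat principle is breached.* Section 6.3.1 defines that population by patients, not observations. Infected patients still contribute earlier visits to the Week 100 model, and a missing Week 104 value is imputed (8.5.3).
- *That the kidney-failure composite will count false events,* because a crossing at the last visit counts as confirmed (9.4.1). This needs last visit to mean last visit with retained data, which no text says. A separate programming conventions document, mentioned in Section 8 and not available here, may settle it.
- *That the exclusion favours bardoxolone.* Without counts and outcomes by arm, the direction is unknown.

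**Conclusion.** The gap is real and worth closing before database lock. Addendum 4.5 drops measured post-infection values from the Year 2 comparisons and by-arm safety tables with no end point, conflicts with SAP Sections 8.8.1, 9 and 9.1.1.1, and leaves no named analysis that keeps them. Addendum 4.5 probably governs, as an express later modification, but that is inference.

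Confidence is high on the text and limited on the effect, because the documents give no infection count. The precision cost is modest under the assumed 2–10%. The effect on the estimate is small when both arms are affected alike, and not necessarily small when they are not; the illustrative cases reach 1.0 mL/min/1.73 m², against a planned Week 104 difference of 4.0. No stated figure in the plan is wrong. The case rests mainly on transparency and on complete by-arm safety reporting.

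**What to change.** In SAP Addendum Section 4.5:

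1. Keep post-COVID safety measurements in the by-arm summaries, flagged, or show those tables with and without them.
2. Prespecify one Week 100 repeated-measures analysis and one Week 104 ANCOVA that retain all observed post-COVID eGFR, reported beside the exclusion versions. Which is primary is the sponsor's choice.
3. Report the number of patients and values excluded, by arm and visit.
4. Reconcile Section 4.5 with SAP Sections 8.8.1, 9 and 9.1.1.1, and state that it applies in the same way to the kidney-failure composite, which is third in the Year 2 testing sequence (Section 8.4).

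The data are already collected. The cost is addendum wording, a flag or second version of the affected safety tables, one additional model run for each of the two eGFR endpoints, and a count table. The retained-value versions will carry a few noisier values. If few patients are affected, they will show that the exclusion made little difference.
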